5.4.2. Examination of Subgroups

The list of subgroups may be used in descriptive summaries and statistical analyses. Additional subgroups of clinical interest may also be considered.

If the percentage of subjects is small within a particular subgroup, then the subgroup categories may be combined.

Subgroup	Categories
Implementation Strategy	
 • Standard • Enhanced
Site	18 European sites
Country	As collected
Gender	
 • Male • Female
Age	
 • ≥50 • <50
Race	
 • White • African Heritage • Asian • Other
CD4 Count	
 • <350 • ≥350

5.5. Other Considerations for Data Analyses and Data Handling Conventions

Other considerations for data analyses and data handling conventions are outlined in the appendices:

Section	Component
13.1	Appendix 1 : Schedule of Activities
13.2	Appendix 2 : Assessment Windows
13.3	Appendix 3 : Study Phases
13.4	Appendix 4 : Data Display Standards & Handling Conventions
13.5	Appendix 5 : Derived and Transformed Data
13.6	Appendix 6 : Reporting Standards for Missing Data
13.7	Appendix 7 : Values of Potential Clinical Importance

6. STUDY POPULATION ANALYSES

6.1. Overview of Planned Study Population Analyses

The study population analyses will be based on the Safety population, unless otherwise specified.

Study population analyses including analyses of subject's disposition, protocol deviations, demographic and baseline characteristics, prior and concomitant medications, and exposure and treatment compliance will be based on GSK Core Data Standards. Details of the planned displays are presented in [Appendix 12: List of Data Displays](#). Enrollment and demographics will be displayed by Implementation strategy, site, country, and overall.

For the two interim analyses based on subjects' 3rd injection data, study population tables and listings will be produced by GSK. Details of these Interim Analysis deliverables can be found in [Appendix 12: List of Data Displays](#).

7. EFFICACY ANALYSES

Implementation Science/Health Outcomes endpoints will form the basis for the overall primary analysis of the study, and details of implementation science/health outcomes analyses are documented in a separate Evidera SAP. Clinical efficacy endpoints are evaluated as secondary objectives for this study.

Efficacy analyses will be performed at Month 12 and EOS. There will be no efficacy reported at the interim analyses.

7.1. Secondary Efficacy Analyses

7.1.1. Endpoint / Variables

- Proportion of participants with Plasma HIV-RNA < 50 copies/mL and plasma HIV-1 RNA \geq 50 copies/mL as per Food and Drug Administration (FDA) Snapshot algorithm at Month 12 (Safety Population). See [Appendix 8](#) for Snapshot Algorithm details.
- Participants with protocol-defined confirmed virologic failure (CVF) over time (Safety population)
- Incidence of treatment-emergent genotypic and phenotypic resistance to CAB and RPV in patient study participants with CVF (Safety population)

7.1.2. Population of Interest

The primary efficacy analyses will be based on the Safety population, unless otherwise specified. HIV-1 RNA summaries will also be reported for the Long-Term Follow-up Population.

7.1.3. Strategy for Intercurrent (Post-Randomization) Events

Participants with last available HIV-1 RNA measurement less than 50 copies/mL while the participant is on treatment within the analysis visit window of interest are classified as HIV-1 RNA < 50 c/mL. Participants without evaluable HIV-RNA data for the visit of interest or who change treatment not permitted per protocol before the analysis window are considered non-responders.

Participants with last available HIV-1 RNA measurement greater or equal to 50 copies/mL while the participant is on treatment within the analysis visit window of interest are classified as HIV-1 RNA \geq 50 c/mL. Participants without evaluable HIV-RNA data for the visit of interest and who discontinue treatment for reasons not related to adverse event while having HIV-1 RNA \geq 50 copies/mL at time of discontinuation or who change study treatment not permitted per protocol before the analysis window are also classified as having HIV-RNA \geq 50 copies/mL.

Missing viral load values for reasons related to COVID-19 issues (e.g. participant is unable to have viral load assessed due to barriers in attending the clinic during the pandemic or COVID-19 related adverse events leading to treatment discontinuation) will

be considered as random missingness and classified the same as all other missingness for the primary efficacy Snapshot analysis. A sensitivity analysis using a modified Snapshot which includes subcategories for Covid-19 related and Non-Covid-19 related missingness will also be performed to display the impact of Covid-19 intercurrent events on the study. See [Appendix 8](#) for Modified Snapshot Algorithm details.

7.1.4. Statistical Analyses / Methods

Details of the planned displays are provided in [Appendix 12](#): List of Data Displays and will be based on GSK data standards and statistical principles.

Unless otherwise specified, endpoints / variables defined in [Section 7.1.1](#) will be summarised using descriptive statistics, graphically presented (where appropriate) and listed.

7.1.4.1. Statistical Methodology Specification

Endpoint / Variables

 • Proportion of participants with plasma HIV-1 RNA < 50 c/mL at Month 12 using the FDA Snapshot algorithm (Safety population) • Proportion of participants with plasma HIV-1 RNA ≥ 50 c/mL at Month 12 using the FDA Snapshot algorithm (Safety population) • Proportion of participants with protocol-defined confirmed virologic failure (CVF) over time (Safety population) • Incidence of treatment-emergent genotypic and phenotypic resistance to CAB and RPV in patient study participants with CVF (Safety population)
Results Presentation

 • The proportion of participants with HIV-1 RNA < 50 c/mL, HIV-1 RNA ≥ 50 c/mL, and with recorded CVF at each planned visit with corresponding 95% confidence intervals calculated using the Clopper-Pearson exact method. • Proportion of subjects with incidence of treatment-emergent genotypic and phenotypic resistance to CAB and RPV in patient study participants with CVF at each visit with corresponding 95% confidence intervals calculated using the Clopper-Pearson exact method. • Descriptive statistics for the nominal values and change from baseline values in CD4+ cell counts and the CD4/CD8 ratio.
Subgroup Analyses

 • Summary of study outcomes will be repeated for subgroups of interest as specified in Section 5.4.2: Implementation strategy, Participant sex, age group (<50 vs ≥50), race (White, African Heritage, Asian, Other), and CD4 count (<350, ≥350). • The proportion of participants in each Snapshot study outcome category and sub-category will be summarized in which default sub-categories have been expanded to present Covid-19 vs. Non-Covid-19 related impact (as described in Appendix 8).

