9.4. Statistical Analyses

There will be two main reporting and analysis timeframes. First, will be the primary complete analyses which will be conducted when the last study participant has completed their CAB LA + RPV LA study treatment up to Dose 7. All study staff participant (site-level) questionnaire and interview data, plus all study participant (subject-level) data will be included in this reporting and analysis effort.

Once all study participants have completed the study, final analyses of the data will also be conducted

The statistical analysis plans will be finalized prior to DBL and it will include a more technical and detailed description of the statistical analyses described in this section. This section is a summary of the planned statistical analyses of endpoints. Analysis on patient

study participant data will account for sites that patients are nested in. The reporting analysis plan will provide further details of the analyses.

As mentioned above, this study has both site- and subject-level outcomes and each outcome will be analyzed and summarized accordingly.

Qualitative interview data will be summarized by a third party and reported as part of the overall study results (CSR). Details of these analyses will be described in a separate analysis plan provided by the CRO partner under GSK's oversight.

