2.1. Changes to the Protocol Defined Statistical Analysis Plan

A change to the originally planned statistical analysis specified in the 213199 protocol [Dated: 06MAY2020] consists of dropping the ITT-E population and introducing the Enrolled population. This is being done as the ITT-E carries the same definition as the Safety population so both populations are not needed. Efficacy is also a secondary endpoint so it would add unnecessary programming work to include an identical

population. The Safety population will serve as the primary population for both safety and efficacy analyses. The Enrolled population is being added in order to adhere to EudraCT standards.

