2.4.1. Sample Size Determination

The study size is based on practical considerations in terms of feasibility of enrolling an adequate number of sites on each implementation strategy balanced with the desire to have interventions tested across several types of investigative sites; as well as enrolling an adequate number of patient study participants in each site.

Approximately 24 sites (from feasibility process) will be selected from the feasibility process to achieve 18 sites randomly assigned to study implementation strategies and approximately 54 evaluable staff study participants for an estimated total of 27 evaluable study staff participants per implementation strategy group.

Assuming 10% screen failures, it is estimated that with 18 sites approximately 527 patient study participants will be screened to achieve 474 subjects enrolled and 450 evaluable patient study participants completing the study (assumes 5% of patient study participants would be non-evaluable) for an estimated total of 225 evaluable patient study participants per implementation strategy group.

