5.4. Examination of Covariates, Other Strata and Subgroups

5.4.1. Covariates and Other Strata

The list of covariates and other strata may be used in descriptive summaries and statistical analyses, some of which may also be used for subgroup analyses. Additional covariates and other strata of clinical interest may also be considered.

Category	Details
Covariates	Implementation strategy, Site, Country, Gender, Age Group, Race, CD4 Count

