13.12.5. Efficacy Tables

Efficacy: Tables					
No.	Population	GSK Standard/ Example Shell	Title	Programming Notes	Deliverable
Snapshot					
2.1.	Safety	EFF T1	Summary of Study Outcomes (50 c/mL cutoff) at Month 12 (Intervention Phase) –Snapshot Analysis		HL, M12
2.2.	Safety	EFF T2	Summary of Study Outcomes (50 c/mL cutoff) at Month 12 (Intervention Phase) –Snapshot Analysis Considering Covid-19 Based Events	With expanded COVID-19 related/Non-related categories	HL, M12
2.3.	Safety	SNAPSHOT4	Proportion of Subjects with Plasma HIV-1 RNA \geq 50 c/mL Over Time (Intervention Phase) –Snapshot Analysis	Use Exact (Clopper-Pearson) method for 95% confidence Intervals. Expand to all visits, drop 'n' row, replace x (%) column data with x/n (%), drop '(Intervention Phase)' and use Observed Case instead of Snapshot for EOS	M12, EOS
2.4.	Safety	SNAPSHOT4	Proportion of Subjects with Plasma HIV-1 RNA < 50 c/mL Over Time (Intervention Phase) –Snapshot Analysis	Use Exact (Clopper-Pearson) method for 95% confidence Intervals. Expand to all visits, drop 'n' row, replace x (%) column data with x/n (%), drop '(Intervention Phase)' and use Observed Case instead of Snapshot for EOS	M12, EOS
2.5.	Safety	SNAPSHOT4	Proportion of Subjects with Plasma HIV-1 RNA \geq 50 c/mL Over Time by Subgroup (Intervention Phase) –Snapshot Analysis	Include the following subgroups: country, implementation arm, sex, age group, race group, and CD4 group as mentioned in Section 5.4.2.	M12

Efficacy: Tables					
No.	Population	GSK Standard/ Example Shell	Title	Programming Notes	Deliverable
2.6.	Safety	SNAPSHOT4	Proportion of Subjects with Plasma HIV-1 RNA < 50 c/mL Over Time by Subgroup (Intervention Phase) –Snapshot Analysis	Include the following subgroups: country, implementation arm, sex, age group, race group, and CD4 group as mentioned in Section 5.4.2.	M12
CVF					
2.7.	Safety	VF1	Cumulative Proportion of Subjects Meeting Confirmed Virologic Failure Criteria Over Time (Intervention Phase)		HL, M12
2.8.	Safety	VF2	Proportion of Subjects Meeting Confirmed Virologic Failure Criteria Over Time		M12, EOS
Genotype & Phenotype					
2.9.	Safety	201584/primary_17/T7.1	Summary of the Prevalence of Treatment-Emergent Major Resistance Mutations of INI, NRTI, NNRTI and PI Class at time of CVF - Plasma Sample	Known resistance mutations per Section 13.5.5. Include 95% confidence Intervals using Exact (Clopper-Pearson) method.	HL, M12, EOS

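### The SAP's Clopper-Pearson intervals for the HIV-1 RNA proportions ignore site, although the protocol says patient analyses will account for it; they are likely too narrow unless the site correlation is very small.

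*SAP*

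**What the plan says.** **The protocol's commitment.** Protocol 9.4 states that analysis on patient "study participant data will account for sites that patients are nested in". The sentence makes no exception for secondary or descriptive endpoints, and it is followed by "The reporting analysis plan will provide further details of the analyses".

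**The SAP's method.** SAP 7.1.4.1 specifies "95% confidence intervals calculated using the Clopper-Pearson exact method" for HIV-1 RNA below 50 c/mL, HIV-1 RNA at or above 50 c/mL, confirmed virologic failure (CVF), and treatment-emergent resistance among patients with CVF. The notes for the HIV-1 RNA tables in SAP 13.12.5 repeat it: "Use Exact (Clopper-Pearson) method for 95% confidence Intervals". The HIV-1 RNA figures in SAP 13.12.6 carry the same note. No site term, design effect or robust variance is given.

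**Where site does appear.** Site is one of the covariates in SAP 5.4.1, but the wording is permissive: "The list of covariates and other strata may be used in descriptive summaries and statistical analyses". It is also a subgroup in SAP 5.4.2.

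**Declared changes.** SAP 2.1 says the change from the protocol's analysis "consists of dropping the ITT-E population and introducing the Enrolled population". SAP 2.1.1 tabulates only that.

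**Size of the trial.** SAP 2.4.1 plans "18 sites randomly assigned to study implementation strategies", with "approximately 527 patient study participants will be screened to achieve 474 subjects enrolled and 450 evaluable patient study participants completing the study".

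**The concern.** Clopper-Pearson is exact for independent patients with a common success probability. Here patients at a site share a clinical team, injection practice and an implementation strategy assigned to the whole site. If outcomes within a site are positively correlated, 450 patients carry less information than 450 independent ones, and the interval overstates how precisely a rate is known beyond these 18 sites.

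Two things are at stake. One is numerical: the actual coverage of the reported 95% intervals, including those by implementation strategy, where each arm has only 9 sites. The other is documentary: someone who reads the SAP's list of changes would conclude that the nesting commitment had been kept.

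**Working it through.** **Plan figures reproduced first.** The documents state no width for the planned proportions. The only patient-level precision given is the half-width in SAP 2.4.1.3 for 225 patients and SD 1: t(0.975, 224) × 1/√225 = 1.9706/15 = 0.131, as stated. The recruitment numbers also reproduce: 450/0.95 = 473.7, rounded up to 474, and 474/0.90 = 526.7, rounded up to 527. None of these contains a cluster term.

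**Inputs.** N = 450 evaluable patients and 18 sites (SAP 2.4.1), so m = 450/18 = 25. Illustrative suppression rates come from Protocol 4.4.2 for the every-8-week regimen: 90% at Week 160 and 94% at Week 96. The ICC is in neither document; 0.01, 0.02 and 0.05 are assumptions.

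**Formulas.** Design effect DE = 1 + (m − 1) × ICC. Effective n = N/DE. Exact limits with x = p × n: lower = Beta quantile 0.025 with parameters (x, n − x + 1); upper = Beta quantile 0.975 with parameters (x + 1, n − x).

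**Widths in percentage points, all patients, before any degrees-of-freedom correction.**

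| ICC | DE | Effective n | Width at 90% | Width at 94% | Width at 2% or 98% |
|---|---|---|---|---|---|
| 0 (as planned) | 1.00 | 450 | 5.8 | 4.6 | 2.8 |
| 0.01 | 1.24 | 363 | 6.4 | 5.2 | 3.2 |
| 0.02 | 1.48 | 304 | 7.1 | 5.7 | 3.5 |
| 0.05 | 2.20 | 205 | 8.7 | 7.0 | 4.4 |

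At 90% the ratios to the planned width are 1.12, 1.23 and 1.51. Within one arm (225 patients, 9 sites) the 90% interval goes from 8.3 points to 9.3, 10.2 and 12.6.

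**Coverage of the planned interval.** Beta-binomial simulation, 18 sites of 25, 100,000 runs:

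| True rate | ICC 0 | 0.005 | 0.01 | 0.02 | 0.05 |
|---|---|---|---|---|---|
| 90% | 95.9% | 94.7% | 93.6% | 90.8% | 83.2% |
| 94% | 95.4% | 93.9% | 92.6% | 89.9% | 82.0% |
| 99% (or a 1% event) | 97.3% | 96.3% | 95.4% | 93.3% | 87.4% |

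The built-in conservatism of Clopper-Pearson therefore absorbs an ICC below about 0.005 at rates of 85% to 98%, and about 0.01 for a 1% event.

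**Degrees-of-freedom correction.** The standard Korn-Graubard interval also multiplies effective n by the squared ratio of t quantiles. With 18 sites this is (1.9653/2.1098)² = 0.868. Even at DE = 1, effective n becomes 450 × 0.868 = 390, and the 90% interval is 6.2 points wide rather than 5.8.

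**The case against.** The strongest reply concerns scope. The nesting sentence is general and names no endpoint or method. Protocol 9.4.2 asks only for the HIV-1 RNA proportions with 95% intervals and gives no site term. The patient comparisons that carry p-values are the acceptability, appropriateness and feasibility scores, and SAP 3 and SAP 7 send survey and health-outcomes analyses to a separate plan that is not available here. The commitment may be honoured there. The virologic endpoints are also secondary and summarised descriptively, with no hypothesis, margin or decision rule.

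This limits the importance of the point but does not remove it. SAP 3 and SAP 7 keep the virologic endpoints in this SAP, so the other plan cannot cure the omission for them. Permission to use site as a covariate, or a breakdown by site, does not adjust a pooled interval.

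Some stronger readings are tempting but unsupported:

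- A reader might infer that any site correlation pushes coverage below 95%. The simulation shows otherwise at very small ICCs.
- A reader might extend the point to resistance. Its denominator is patients with CVF. At an illustrative 2% that is 0.02 × 450 = 9 patients over 18 sites, so a cluster size of 25 and the design effects above do not apply.
- A reader might take the ICC of 0.05 as expected. It implies a between-site SD of √(0.05 × 0.9 × 0.1) = 6.7 points at 90%, and √(0.05 × 0.02 × 0.98) = 3.1 points around a mean of 2%. The latter is extreme for a rare event.

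**Conclusion.** The mismatch between Protocol 9.4 and SAP 7.1.4.1 is plain, undeclared, and does not depend on any ICC. The numerical consequence does. For the two HIV-1 RNA proportions, and secondarily for CVF, the intervals are likely too narrow once the ICC exceeds the small values that Clopper-Pearson absorbs. The assumed range gives 12% to 51% extra width at 90%, and more with a degrees-of-freedom correction. These figures assume 18 equal sites of 25 and inference beyond those sites; unequal site sizes would raise the design effect. The documents do not support a claim that the virologic point estimates are biased or that the staff-score hypothesis is affected. This should be corrected, but no primary conclusion rests on it.

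**What to change.** **Preferred.** In SAP 7.1.4.1, and in the notes to the HIV-1 RNA tables and figures in SAP 13.12.5 and 13.12.6:

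- Specify a site-adjusted interval for the HIV-1 RNA proportions, overall and by implementation arm. One option is an exact interval at the effective sample size from the estimated between-site variance, with the design effect floored at 1.
- State whether a degrees-of-freedom correction for the number of sites is applied. Without it, the floored interval equals Clopper-Pearson when no site effect is estimated; with it, it does not.
- Report the estimated ICC.
- For CVF and resistance, fall back to Clopper-Pearson when events are too few to estimate between-site variance.
- Keep Clopper-Pearson for the HIV-1 RNA proportions as a supporting display.

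**Minimum.** If Clopper-Pearson stays as the main interval, list the departure in SAP 2.1.1 with a reason and add the site-adjusted interval as a sensitivity analysis.

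**Cost.** Minor programming and no new data. Intervals will be wider by an amount that depends on the ICC; at 0.05 the widening is about half, which is not slight.

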8. SAFETY ANALYSES

The safety analyses will be based on the Safety and Long Term Follow-up (LTFU) populations, unless otherwise specified.

For the interim analyses, adherence to dosing will be reported for the Safety population. For the Month 12 primary analysis, outputs will be presented for the Safety population in the Intervention Phase unless otherwise specified. For the EOS analysis, outputs will be presented for the Safety population in the Intervention and Extension phases as well as for the LTFU population in the LTFU phase.

For the Month 12 analysis, a set of separate outputs will also be presented for the oral lead-in period, including a summary of adverse events, SAEs, AEs leading to withdrawal, post-baseline emergent chemistry/haematology abnormalities, and subjects with hepatobiliary abnormality criteria.

8.1. Safety Endpoints

Secondary and tertiary safety endpoints for this study include:

- Percentage of injections occurring within target window from the target date.
- Incidence and severity of AEs and SAEs over time

CCI

r time

8.2. Adverse Events Analyses

Adverse events analyses including the analysis of adverse events (AEs), Serious (SAEs), Drug-related AEs, AEs leading to withdrawal, AEs by maximum severity, COVID-19 AEs, and other significant AEs will be based on GSK Core Data Standards. The details of the planned displays are provided in [Appendix 12](#): List of Data Displays.

CCI

CCI

8.3. Adverse Events of Special Interest Analyses

A comprehensive list of MedDRA terms based on clinical review will be used to identify Adverse Events of Special Interest (AESI). Changes to the MedDRA dictionary may occur between the start of the study and the time of reporting and/or emerging data from on-going studies may highlight additional adverse events of special interest, therefore the list of terms to be used for each event of interest and the specific events of interest will be based on the safety review team (SRT) agreements in place at the time of reporting. The details of the current planned grouping, including Standardized MedDRA Query (SMQ) values (as applicable), and planned displays are provided in [Appendix 9](#): AESI identification and [Appendix 12](#): List of Data Displays.

8.4. Clinical Laboratory Analyses

Laboratory evaluations including the analyses of Chemistry laboratory tests and Hematology laboratory tests will be based on GSK Core Data Standards. The details of the planned displays are in [Appendix 12](#): List of Data Displays.

8.5. Other Safety Analyses

The analyses of injections in the target window as well as non-laboratory safety test results including vital signs will be based on GSK Core Data Standards, unless otherwise specified. The details of the planned displays are presented in [Appendix 12](#): List of Data Displays.

